#### **Electronic Consent (e-Consent) and Assessments:**

To securely and efficiently maintain the data collected for this study, an electronic (eREG) binder will be utilized. As described below, paper regulatory documents will be scanned, verified, and filed in the eREG folder. To optimize the eREG process, electronic consent and assessments can be utilized. The format of electronic regulatory documents include pdf and/or REDCap. In addition to facilitating questionnaire distribution and document management, REDCap will enhance data analysis. Digital consent forms and questionnaires can be distributed to the participants/families who have reliable access to internet/email. Completion of electronic questionnaires and/or signing of e-Consent documents may take place during study visits using CCHMC resources (tablet, computer, signature pad) currently available to the study team.

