**Kiddie Schedule for Affective Disorders and Schizophrenia (K-SADS)**

The KSADS is compatible with the DSM-5 and has been validated in multiple research and treatment settings. The KSADS cross-cutting measure (DSM-5 CC-SM) is an abbreviated version of the extended form. The abbreviated measure is a reliable way to recognize mood, anxiety, psychotic, and disruptive behavior disorders and is a useful screen for eligibility of potential participants. The DSM-5 CC-SM are designed to be self-report measures, completed by the parent and child. The assessment typically is completed in 10 minutes.

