**Review of anxiety, depression, and C-SSRS responses and referral for clinical evaluation:**

Study doctor (or designee) will verbally administer and then review each suicide assessment. The 'Columbia-Suicide Severity Rating Scale Screen with Triage Points' document outlines the planned course of action based on the participant's response. In particular, if a participant/family discloses any suicide ideation at any point in this study, the study staff will contact the participant's mental health provider or primary care provider and/or *Psychiatric Intake Response Center (PIRC)* at CCHMC for further assessment and guidance within 24 hours.

*The Pediatric Intake Response Center (PIRC) manages psychiatric patient consultation and intake for Cincinnati Children's Hospital Medical Center. Staff members are available 24 hours a day, seven days a week at [contact] or [[contact]](mailto:[contact]).*

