**Table 4: Schedule of Assessments**

	Visit 1	Visit 2				Visit 3		Visit 4
	Screening	Baseline	Abbreviated Remote monitor and safety	Remote monitor and safety	Abbreviated Remote monitor and safety	End Intervention	Remote monitor and safety	Follow Up
Task	Week 0	Week 1	Week 2	Week 4	Week 6	Week 8	Week 10	Week 12
Review Eligibility Criteria $\Psi$	X							
KBIT-2 (Kaufman Brief Intelligence Test, Second Edition) $\Psi$	X							
KSADS (MedHis)	X							
Cognitive Function Screening $\Psi$	X							
Test dose	X							
Informed Consent $\Psi$	X							
Brain Imaging (MRI/MRS) $\Psi$		X				X		X
Urine Pregnancy (Females only)	X	X						
Vitals*		X				X		X
Safety labs*		X				X		X
Physical Exam*		X				X		X
ADHD-RS (DuPaul) $\Psi$		X		X		X	X	X
KSADS (CC)		X		X		X	X	X
PARS (Pediatric anxiety rating scale)		X		X		X	X	X
CDRS (Children's depression rating scale)	X	X		X		X	X	X
C-SSRS (Columbia Suicide Severity Rating Scale)	X	X		X		X	X	X
Wechsler Intelligence Scale for Children, Fifth Edition (WISC-V) $\Psi$	X	X				X		X
Behavioral Rating Inventory of Executive Function (BRIEF-2) $\Psi$		X				X		X
Test of Variables of Attention (TOVA) $\Psi$		X				X		X
PANESS scale $\Psi$		X				X		X
TMS assessment $\Psi$		X				X		X
NAC/Placebo Prescription		X						
Med Log		X	X	X	X	X	X	X
AE assessment (MedDRA)		X	X	X	X	X	X	X
Follow-up plan								X

\* Indicates clinical procedures performed as standard of care

$\Psi$  Indicates research procedures to be completed in both treatment and non-treatment cohorts

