**COMPLIANCE AND SAFETY MONITORING:**

Monitoring and Managing Adherence to Treatment:

Pill/Sachet counts and/or review of the medication log will be used to estimate compliance, along with queries about missed doses. We will require a standard of four days out of seven on treatment to obtain a rating but will counsel the participant and family about the importance of adherence in such a situation. We will require a minimum of 5 days per week on treatment in each of the final two weeks of each treatment block, so that the end-of-treatment ratings are an accurate reflection of treatment. For the final study visit and pTMS assessment, subjects must have 100% compliance for the two days prior to testing or testing will be rescheduled within a reasonable 3-4 day window so that compliance can be assured.

Communication:

To facilitate data collection, safety monitoring, and accommodate preferences of participants, communication between study staff and the research participant/family/teachers will utilize a variety of technologies. Modes of communication may include phone calls, videoconference, electronic mail (e-mail), REDCap surveys (via e-mail link or Twilio text message), and in person meetings. Responses to safety assessments will be reviewed by a member of the study team within 48 hours. As described elsewhere, if a participant/family discloses any suicide ideation or significant health concerns at any point in this study, the study staff will contact the participant's mental health provider or primary care provider and/or Psychiatric Intake Response Center (PIRC) at CCHMC for further assessment and guidance within 24 hours.

Video recordings may aide recruitment and explanation of study assessments/details. These recordings may be distributed in a similar manner to other advertisements (websites, philanthropic/educational events, through interactions related to clinic visits, distributed via REDCap correspondence, et cetera). Examples or video content would be a short description of TMS and PANESS procedures. A general outline of the study (risks/benefits, procedures, timeline, et cetera) as would be described during informed consent would also be advantageous.

Medical/safety assessments:

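### A 48-hour review window for safety responses is too long beside a 24-hour escalation limit wherever a response is submitted unattended; the residual risk is small and the fix is cheap

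*Combined protocol and SAP*

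**What the plan says.** Three statements follow one another in Compliance and Safety Monitoring, Communication, in a paragraph whose stated purposes include safety monitoring.

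- On channels: "Modes of communication may include phone calls, videoconference, electronic mail (e-mail), REDCap surveys (via e-mail link or Twilio text message), and in person meetings".
- On review: "Responses to safety assessments will be reviewed by a member of the study team within 48 hours".
- On escalation: if a participant or family "discloses any suicide ideation or significant health concerns at any point in this study", staff must contact the child's mental health provider, primary care provider and/or PIRC within 24 hours.

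The section on review of anxiety, depression and C-SSRS responses gives the same 24-hour limit for suicide ideation ("if a participant/family discloses any suicide ideation at any point in this study, the study staff will contact" the provider or PIRC). There it follows a C-SSRS that the study doctor or designee gives verbally and then reviews. Neither section says when the 24 hours begin.

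Other parts of the protocol bear on how responses may arrive.

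- The K-SADS section says of the abbreviated cross-cutting measure: "The DSM-5 CC-SM are designed to be self-report measures, completed by the parent and child". On its purpose: "The abbreviated measure is a reliable way to recognize mood, anxiety, psychotic, and disruptive behavior disorders".
- Table 4 schedules KSADS (CC) at baseline and weeks 4, 8, 10 and 12. The columns for weeks 4 and 10 are headed "Remote monitor and safety".
- The e-Consent section says: "Digital consent forms and questionnaires can be distributed to the participants/families who have reliable access to internet/email".

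**The concern.** When an assessment is given live, disclosure and staff awareness happen together, and a 24-hour escalation rule works as intended. When a form or message is sent in with nobody present, the two separate, and the time before anyone reads it matters. The only review time stated for written safety responses is 48 hours, twice the escalation limit that follows it, and no shorter time is set for answers that signal trouble.

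Staff who keep to the written rule could therefore leave a report of a significant concern about a child aged 8 to 16 unread for two days. No other section sets a faster review of written responses. Study Design mentions a medical safety monitor without review times, Data Safety and Monitoring says there is no external monitor, and non-serious adverse events are reviewed quarterly.

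**Working it through.** **Inputs**

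- Review window: 48 h (Communication). Its start is not stated; I assume it runs from receipt, and that receipt coincides with submission and disclosure.
- Escalation limit: 24 h (Communication, and the section on review of C-SSRS responses). Its start is not stated.
- For comparison, Measurement and Management of Adverse Effects gives 24 h for reporting serious events to the IRB, counted from awareness.

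**Time from an unattended disclosure to required contact, current text**

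1. Clock from awareness: 48 h + 24 h = 72 h at the latest.
2. Clock from disclosure: a response read at hour *t* leaves 24 − *t* hours. At *t* = 24 nothing is left. At *t* = 48 the result is 24 − 48 = −24, so the limit passed 24 h earlier.

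The first reading is tenable, since the IRB rule uses awareness. Under it the two limits run in sequence and do not contradict each other. Under the second, any review between hours 24 and 48 complies with one rule and breaks the other.

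**With review within 24 h of receipt**

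1. Clock from awareness: 24 h + 24 h = 48 h, which is 72 − 48 = 24 h sooner.
2. Clock from disclosure: a review at hour 24 leaves 24 − 24 = 0 h, so the limit could only just be met. This is one reason to add an immediate alert.

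**How many responses could be affected (Table 4)**

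| Instrument | How given, per the protocol | Time points |
|---|---|---|
| KSADS (CC) | self-report by parent and child | baseline, weeks 4, 8, 10, 12 |
| C-SSRS | verbal, then reviewed | screening and the same five |
| CDRS | clinician, interviews with parent and child | screening and the same five |
| PARS | clinician-rated after interview | the same five |
| AE assessment | mainly by questioning | the same five, plus weeks 2 and 6 |

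KSADS (CC) has 5 time points. Visits 2, 3 and 4 account for baseline, week 8 and week 12, which leaves 5 − 3 = 2 remote ones (weeks 4 and 10). I assume that KSADS (CC) counts as a safety assessment, because it sits in the remote safety columns. The share completed unattended is not given, so remote exposure through this form is 0 to 2 time points per treated child, plus any AE replies taken by survey. At weeks 2 and 6, AE assessment is scheduled without the C-SSRS, CDRS or PARS, so a survey reply there would lack a scheduled mental-health interview beside it.

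**The case against.** The strongest answer is that no section says any safety instrument is completed unattended. Self-report is not the same as unattended, and a remote contact may be a phone or video call. The exposure range includes zero. This stands, and it limits the point to responses that do arrive unattended.

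Second, every KSADS (CC) time point also carries a verbal C-SSRS, two clinician interviews and AE assessment. Suicidality, depression, anxiety and general health should therefore be asked about live at those points. This also stands. What is left is a concern written down but not raised in an interview, a form sent on a different day from the interviews, an AE reply by survey, or a free-text e-mail. Exclusion by history of major depression, bipolar disorder and other psychiatric diagnoses lowers the expected frequency further.

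Third, 48 hours is a ceiling, and 72 hours needs both ceilings to be fully used. That is so; 72 hours is an outer bound and not an expected delay. Nor do the documents supply a standard that makes 24 hours right and 48 wrong. The case for 24 rests on the plan's own escalation limit.

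A reader might infer more: that the plan lets suicide ideation go unread for days, or that its two limits flatly contradict each other. The documents support neither. The dedicated suicide screen is verbal, and the protocol does not say whether KSADS (CC) asks about suicide. The C-SSRS triage document that the protocol cites is not among the documents, so any timing it sets is unknown. The limits conflict only if the 24 hours run from disclosure, which the text does not say.

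**Conclusion.** The point holds as a cheap improvement. The written rule permits an unattended safety response to wait 48 hours, and so to use up or exceed the 24-hour escalation limit. The outer bound is 72 hours to contact with an awareness clock, or 24 hours past the limit at the latest permitted review with a disclosure clock. The conclusion assumes that some safety responses arrive unattended, which the Communication paragraph allows but does not establish, and that the 48-hour rule covers them.

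The residual risk is small because live assessment is scheduled at all five KSADS (CC) time points. The missing start of the 24-hour clock is a matter of wording and would not justify the point by itself. Confidence is medium, because the route and frequency of unattended collection are not stated.

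**What to change.** In Compliance and Safety Monitoring, Communication, replace the 48-hour window, for safety responses submitted unattended, with review within 24 hours of receipt. Support it with an automated REDCap alert to the study doctor or designee when a form carries a concerning answer. Alternatively, collect those items live by phone, video or in person. If the site already does either, writing it down settles the matter.

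An alert will not catch free-text e-mail, so tell families to use the existing round-the-clock PIRC line for urgent concerns. As a clarification only, state in that paragraph and in the section on review of C-SSRS responses that the 24-hour escalation limit runs from staff awareness.

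The cost is one or two sentences, the alert set-up and occasional out-of-hours review. Endpoint, sample size and analysis do not change.

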**Table 6: Medical Dictionary for Regulatory Activities (MedDRA)**

MedRA System organ class	MedDRA preferred term
Nervous system disorders	Headaches, Dyskinesias, Disturbances in initiating and maintain sleep,

Psychiatric Disorders	Anxiety symptoms, decreased or increased physical activity levels, depressive symptom
Gastrointestinal Disorders	Nausea, vomiting, constipation

### Dose Modification:

#### Definition of Dose-Limiting Toxicity (DLT)

DLT will be defined as any of the following events that are at possibly, probably or definitely attributable to therapy. Adverse events will be graded using CTCAE v5.0.

### Dose Modification

Dose reductions and/or withholding of doses must be based on the following:

- Dose reduction to half dose (35mg/kg/day) to be determined by study doctor or designee (**Table 7**)
- General dose modification guidelines for clinically significant toxicities considered related to treatment are provided in **Table 8**
- Local medical practice and regional regulatory guidance.

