### **STUDY DESIGN:**

This is a prospective single-center; randomized, double-blind, placebo-controlled Phase II study to determine the safety and efficacy of NAC on motor behavior and/or attention deficits of children with NF1 aged 8 to 16 years. Participants will be randomized to 8-weeks of treatment with NAC (70 mg/kg/day) versus placebo. This is a collaborative study between multiple specialties at CCHMC and external collaborators at Children’s National Hospital and Technion Israel Institute of Technology. We have received IND approval from the FDA to use NAC for the application in this study (IND# 139468).

It is plausible and ethical to employ a placebo group, as no standard therapy with established efficacy is being withheld. There is no crossover in this study due to a lack of data concerning the length of possible washout effects. Primary and secondary outcome measures will be administered at baseline, after 8 weeks of treatment and at follow-up, 4 weeks after cessation of treatment to determine any washout effects.

In addition, the effect of NAC on measures of impulsivity, attention, executive function, and SICI and imaging biomarkers will be assessed. Participants will be carefully monitored for side effects by a medical safety monitor for the study. The safety of NAC will be evaluated using laboratory tests, clinical signs and adverse effects, which will be monitored at regular intervals over the 8-week treatment period.

An additional cohort of age/sex-matched NF1 participants will be recruited in order to characterize and validate biomarkers of brain function.

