### **Treatment with NAC:**

For this single center randomized double-blind placebo controlled, prospective, Phase II study, each subject will be dosed with approximately 70 mg/kg/day of NAC for 8 weeks. To facilitate drug compounding, three tiers of drug dose will be administered based on body weight as described in **Table 3**.

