**Table 3: NAC Dosing**

Participant's weight (kg)	Dose (BID)
< 20	700 mg
20-40	1050 mg
> 40	1350 mg

\*Max dose not to exceed 2700mg/day (1350mg BID)

We have treated 5 patients off-label with NAC at 900 mg twice daily with improved behaviors without side effects. NAC is a natural supplement that acts as an antioxidant and a glutamate modulating agent. It is widely available over the counter. We have received IND approval from the FDA to use NAC for the application in this study (IND# 139468).

To mitigate potential non-compliance, participants will be given a 'test dose' of the study placebo (capsule and/or powder) at the screening visit. If prescribed encapsulated drug, they will have to demonstrate that they can swallow the capsule. If prescribed powder, they will have to demonstrate that they can drink the powder without any issues.

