#### Justification for Dose Modification

Previous studies have shown oral NAC administration to humans at 35 mg/kg and 70 mg/kg produced CSF concentrations above the required biological activity in the brain. Therefore, it has been established that at 35mg/kg/day, NAC passes the blood brain barrier and would be efficacious as a neurocognitive therapy.

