**Table 8: General Dose Modification Guidelines**

CTCAE Grade	Action and Dose Modification
Grade 1	
 
• Continue treatment at current dose level
 
• Monitor closely
 
• Provide supportive care according to institutional standards
 

Grade 2	
 
• Interrupt treatment if clinically indicated
 
• Monitor closely
 
• Provide supportive care according to institutional standards
 
• When toxicity resolves to grade 1 or baseline, restart treatment at current dose level
 

Grade 3	
 
• Interrupt treatment
 
• Monitor closely
 
• Provide supportive care according to institutional standards
 
• When toxicity resolves to grade 1 or baseline, restart treatment reduced by half
 

Grade 4	
 
• Interrupt treatment
 
• Monitor closely
 
• Provide supportive care according to institutional standards
 

	

• Restart with treatment reduced by half once toxicity resolves to grade 1 or baseline

• If the grade 4 toxicity recurs, permanently discontinue treatment

--	--

The occurrence of adverse events should be sought by non-directive questioning of the patient at each visit during the program. Adverse events also may be detected when they are volunteered by the patient during or between visits or through physical examination, laboratory test, or other assessments. All adverse events must be recorded in an agreed-upon format, such as on the Adverse Event Form, which will be provided with the following information:

1. Severity grade (mild, moderate, severe)
2. Relationship to the drug(s) of interest (suspected/not suspected)
3. Duration (start and end dates or if continuing at final exam)
4. Whether it constitutes a serious adverse event (SAE)

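### The reduced dose is stated as 35 mg/kg/day, but half of the assigned Table 3 dose equals that figure only at 30 kg

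*Combined protocol and SAP*

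**What the plan says.** The Study Design section gives the regimen per kilogram: "Participants will be randomized to 8-weeks of treatment with NAC (70 mg/kg/day) versus placebo". The section on treatment with NAC softens this, stating that "each subject will be dosed with approximately 70 mg/kg/day of NAC for 8 weeks", and then moves to fixed doses: "To facilitate drug compounding, three tiers of drug dose will be administered based on body weight". Table 3 sets 700 mg twice daily below 20 kg, 1050 mg twice daily at 20-40 kg and 1350 mg twice daily above 40 kg, with the limit "Max dose not to exceed 2700mg/day (1350mg BID)".

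The reduced dose is described in three places:

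- The Dose Modification section says "Dose reduction to half dose (35mg/kg/day) to be determined by study doctor or designee" and refers to Table 7.
- Table 7 lists level 0 as 70 mg/kg/day and level -1 as 35 mg/kg/day. It does not mention the tiers or say that the figures are approximate.
- Table 8 says that after grade 3 or grade 4 toxicity has resolved, treatment restarts "reduced by half". It gives no figure in mg or mg/kg.

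The justification for the reduced dose rests on the statement that "oral NAC administration to humans at 35 mg/kg and 70 mg/kg produced CSF concentrations above the required biological activity in the brain". No section gives the reduced dose in mg for each tier, and none says which description governs if they differ.

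**The concern.** The Dose Modification text treats half of the dose and 35 mg/kg/day as the same thing. That would be true if children received 70 mg/kg/day, but they receive a tier dose, which per kilogram varies widely with weight. A prescriber who halves the assigned dose and one who calculates 35 mg/kg/day will reach different amounts for almost every child.

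This is a dose instruction for children with toxicity, and it is left to whoever is acting as study doctor. Following the mg/kg figure would cut the dose by less than half in children above 30 kg and by more than half in children below 30 kg. Following the halving rule gives an amount that differs from the one printed in Table 7 and cited in the justification.

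**Working it through.** **Inputs.** The twice-daily doses and weight tiers are from Table 3, and levels 0 and -1 are from Table 7. The weights below are illustrative, because the documents give no weight distribution for the trial population.

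**The plan's own figure.** 70 / 2 = 35 mg/kg/day. The stated half dose reproduces from Table 7's nominal level 0.

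**Tier doses per day.** 2 x 700 = 1400 mg (<20 kg); 2 x 1050 = 2100 mg (20-40 kg); 2 x 1350 = 2700 mg (>40 kg). The halves are 700, 1050 and 1350 mg/day.

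**Where half the tier dose equals 35 mg/kg/day.** Solve (half tier dose) / weight = 35 within each tier:

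- <20 kg: 700 / 35 = 20.0 kg, which is outside the tier because 20 kg belongs to the next one.
- 20-40 kg: 1050 / 35 = 30.0 kg, which is inside the tier.
- >40 kg: 1350 / 35 = 38.6 kg, which is outside the tier.

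The only solution is 30 kg.

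**The two readings compared.** The literal dose is 35 x weight, and the literal cut is 1 - (35 x weight) / (tier dose). Under halving, the cut is 50% at every weight.

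| Weight (kg) | Tier dose (mg/day) | 35 mg/kg/day (mg/day) | Half tier (mg/day) | Literal cut | Half tier (mg/kg/day) |
|---|---|---|---|---|---|
| 20 | 2100 | 700 | 1050 | 67% | 52.5 |
| 30 | 2100 | 1050 | 1050 | 50% | 35.0 |
| 40 | 2100 | 1400 | 1050 | 33% | 26.3 |
| 50 | 2700 | 1750 | 1350 | 35% | 27.0 |
| 60 | 2700 | 2100 | 1350 | 22% | 22.5 |

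The literal cut falls to zero at 2700 / 35 = 77.1 kg.

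**How close is close enough.** Half the tier dose lies within 10% of 35 mg/kg/day (31.5 to 38.5) only in these weight ranges:

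- 700 / 38.5 = 18.2 kg to just under 20 kg
- 1050 / 38.5 = 27.3 kg to 1050 / 31.5 = 33.3 kg
- just over 40 kg to 1350 / 31.5 = 42.9 kg

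**Against the cited support.** Between 30 and 40 kg, half the tier dose falls from 35 to 1050 / 40 = 26.25 mg/kg/day. Above 40 kg it is always below 1350 / 40 = 33.75 mg/kg/day. It is therefore below 35 mg/kg/day at every weight over 30 kg.

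**The case against.** The strongest reply is that 35 mg/kg/day is a label. The treatment section calls 70 mg/kg/day approximate and explains that the tiers exist to ease compounding. Given Table 3 and its cap, level 0 in Table 7 can only be nominal, and level -1 is simply half of it in the same two-row table. Giving each child exactly 35 mg/kg/day would need the individual compounding that the tiers are there to avoid. Any stepped dose table matches its nominal per-kilogram value only at isolated weights, and 70 / 2 = 35 is not a miscalculation. Most of this stands, and it makes halving the likely intent. It does not remove the conflict. The qualifier is absent from the Dose Modification text and from Table 7, and over most of the weight range the gap is larger than 10%.

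Three stronger readings are tempting, and the documents do not support them.

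- A reader might infer that a 60 kg child with grade 3 or 4 toxicity would receive only a 22% cut. Table 8 sets the action for those grades and says "reduced by half" with no per-kilogram figure, so on its own terms it gives a 50% cut at any weight. The 22% arises only if Table 7's figure is carried into Table 8.
- A reader might infer that halving gives an inactive dose above 30 kg. The justification reports adequate CSF levels at 35 and 70 mg/kg. It does not call 35 mg/kg a minimum, so it says nothing directly about lower doses.
- A reader might infer that starting doses or the treatment comparison are compromised. Starting doses are set in mg by Table 3 and do not depend on level -1.

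**Conclusion.** The point holds as a minor inconsistency in dose specification. The figure of 35 mg/kg/day agrees with half of the assigned dose at 30 kg and at no other weight. If followed as written, it would over-reduce the dose below 30 kg and under-reduce it above, with no reduction from about 77 kg. The arithmetic rests only on Table 3 and Table 7.

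How often this would matter cannot be estimated, because the documents give neither participants' weights nor an expected number of dose reductions. Only children whose dose is reduced are affected. Starting doses, sample size and the randomised comparison are not. The likely reading, halving the assigned dose, already gives the intended cut, which is why the point ranks as minor.

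**What to change.** In the Dose Modification section and Table 7, define level -1 as half of the assigned Table 3 dose: 700 / 2 = 350 mg, 1050 / 2 = 525 mg or 1350 / 2 = 675 mg twice daily, by tier. Delete 35 mg/kg/day there or mark it as nominal. Table 8 then needs no change.

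In the Justification for Dose Modification, add that half the tier dose is below 35 mg/kg/day above 30 kg, so the cited CSF data do not directly cover it there, and that this does not show the lower dose to be inactive.

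The cost is a wording change. The one real downside is that the protocol would openly lose its direct cited support for the reduced dose in children above 30 kg.
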